8.6 Cardiac Assessments

Cardiac assessments including electrocardiogram (ECG) and echocardiogram (ECHO) assessment date and results along with clinically significance will be presented in data listings.hriv

8.7 ECOG Performance Status

ECOG performance status scores will be summarized for baseline, and worst-case shift from baseline in a table and presented in a data listing.

8.8 Blood Phenotype and Direct Antiglobulin Test

Blood phenotype and direct antiglobulin test (DAT) assessment date and result will be presented in a data listing.

8.9 Transfusion

Transfusions data will be presented in a data listing.

9. PHARMACOKINETIC ANALYSES

The merge of SL-172154 serum concentration with CRF data will be performed after database lock by Shattuck Labs to generate a dataset with actual PK sampling times, actual time relative to

the start of infusion, and SL-172154 concentrations. Derivation of PK parameters will be performed by using Phoenix WinNonlin (Version 8.2 or higher).

Unless otherwise specified, all PK data analysis will be based on the PK population and summarized by dose levels regardless of dosing schedules. Subjects who have infusion outcome as "Not Completed" on the PK sample collection day will be included in the summary of dose normalized concentration and PK parameter but will be excluded from other summary by dose level for the corresponding PK sample collection day.

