3.3 SL-172154 Dose Escalation Plan

Dose escalation will begin on Schedule 1 at the starting dose of 0.1 milligrams per kilogram (mg/kg) as outlined in Table 1 below. Intermediate or higher dose levels not shown may be explored based on emerging data (e.g., safety and pharmacodynamic data). Dose escalation of SL-172154 will not exceed half-log increments. The DLT assessment period is 28 days in length and ends 14 days after the last dose is administered in the first cycle on Schedule 1 and 7 days after the last dose is administered on Schedule 2. Dose escalation will follow the mTPI-2 decision rules outlined in Table 7 in Section 9.1.

- Schedule 1 administration for SL-172154: Given on days 1, 8, and 15 in cycle 1 over 28 days and then every two weeks thereafter on days 1 and day 15 in cycles \geq 2 every 28 days.
- Schedule 2 administration for SL-172154: Given on days 1, 8, 15 and 22 of each 28-day cycle
- Cycle length for Schedules 1 and 2: 28 days
- **DLT assessment period for Schedules 1 and 2**: 28 days

Table 1: SL-172154 Dose Escalation Plan in Phase 1
--

	Dose LevelIV Dose of SL-172154 (mg/kg) ^{a,b,c,d,e} Duration of Infusion ^d				
Lev	evel 1 - starting dose 0.1 30 minutes (+/- 10 minutes)				
Lev	vel 2	0.3	30 minutes (+/- 10 minutes)		
Lev	vel 3	1.0	30 minutes(+/- 10 minutes)		
Level 4 3.0 60 minutes (+/- 15 minutes)					
Level 5 10.0 60 minutes (+/- 15 minutes)					
a) b)	cycle 1 and then on days Dose escalation on Sched once weekly on days 1, 8	1 and 15 in cycles \geq 2. Jule 2 may be tested: If Schedule 2 is of , 15, and 22 of each 28-day cycle.	in 28-day cycles on days 1, 8, and 15 in pened, SL-172154 may be administered		
c) d)	kg. For subjects with body weight >100 kg, the dose to be administered should be the same as that calculated for a subject weighing 100 kg (see Section $5.1.4$).				
e)	Infusion time may change based on final drug volume needed for administration, safety and tolerability of the infusion for the subject and/or observed safety findings during the study. Please refer to the Study				

Pharmacy Manual (SPM) for details.

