9.2.3 General Data Analysis Consideration

Tabular summaries will be presented by dose levels/schedule/cohorts and total number of subjects in the corresponding population. Categorical data will be summarized by the number and percentage of subjects in each category. Continuous variables will be summarized by descriptive statistics.

As it is anticipated that accrual will be spread thinly across centers and summaries of data by center would be unlikely to provide valuable information, data from all participating centers will be pooled prior to analysis.

All data up to the time of study completion/withdrawal from study will be included in the analysis for each subject, regardless of duration of treatment.

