9.2.7 Pharmacodynamics Analyses

The pharmacodynamic analysis will be based on the pharmacodynamic population. Pharmacodynamic biomarkers values will be summarized descriptively by dose level, schedule and visit.

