3.1 Study Design

This Phase 1 FIH study is to evaluate the safety, PK, pharmacodynamic effects, and anti-tumor activity of SL-172154 monotherapy. Subjects with platinum ineligible ovarian, fallopian tube, and

primary peritoneal cancers are eligible for treatment. This study includes dose escalation, pharmacodynamic, and dose expansion cohorts (see Schema below).

Study Design: Phase 1 Study of SL-172154 (SIRPα-Fc-CD40L)

Primary objectives: Safety and tolerability of SL-172154

Secondary objectives: RP2D, PK, immunogenicity and anti-tumor activity / Exploratory objectives: PD markers in blood and tumor

Tumor type: platinum-ineligible ovarian, fallopian tube and primary peritoneal cancers

Dose Escalation and Dose Expansion Study (N~33-54 Subjects)

Dose Escalation Rules:	mTPI-2	Dose Level	SL-172154 IV Dose (mg/kg)*	Dose Expansion	RP2D
		Start: 1	0.1	Further assessment	Decision
DLT Assessment Period:	28 days	2	0.3	of SL-172154 on a schedule at	Based on totality
		3	1.0	select dose(s)	of data
Subjects per Cohort:	≥3	4	3.0		Safety, PK, PD and anti-tumor activity
		5	10.0	PD Cohort	

*Evaluation of SL-172154 Dosing on Two Potential Schedules:

Schedule 1: once weekly (D1, D8, D15) q28 days in cycle 1, then q2wks thereafter (D1, D15) q28 days in cycle 2 and beyond Schedule 2: once weekly (D1, D8, D15, D22) q28 days in each cycle

Abbreviations: D = day; DLT = dose limiting toxicity; IV = intravenous; mTPI-2 = modified toxicity probability interval-2; PD = pharmacodynamic; PK = pharmacokinetics; q2wks = once every 2 weeks; RP2D = recommended phase 2 dose

Dose Escalation Cohorts

During dose escalation, two possible schedules (Schedule 1 and Schedule 2) for administration of SL-172154 may be explored as outlined below:

- Schedule 1: SL-172154 is given on days 1, 8 and 15 in cycle 1 (28 days for each cycle) and then every 2 weeks thereafter on days 1 and 15 in cycles >=2
- Schedule 2: SL-172154 is given on days 1, 8, 15 and 22 each 28-day cycle

Dose escalation for Schedule 1 and Schedule 2 will utilize the modified Toxicity Probability Interval (mTPI-2) design as described by Guo et al. with target DLT rate of 30% for the MTD. Subjects will be enrolled in cohorts of approximately 3 subjects into sequential dose levels of SL-172154 and evaluated for DLT during the 28-day DLT evaluation period starting from the first dose of SL-172154. At each dose level, a minimum 3-day stagger between dosing the first and second subject is required.

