11. CHANGE FROM PROTOCOL-SPECIFIED ANALYSES

There are four changes from protocol-specified analyses:

- 1. Protocol Section 9.2.3 states that tabular summaries will be presented by dose levels/schedule/cohorts. Due to the limited enrollment, data from different cohorts will be pooled and summarized by schedule/dose level.
- 2. It is clarified in SAP Section 4 that the DLT Evaluable Population derivation is for the subjects enrolled in the dose escalation cohorts.
- 3. It is clarified in SAP Section 4 that all subjects who have signed the main study inform consent form are defined as Screened population, instead of Enrolled population.
- 4. "postdose" was added in SAP Section 4 for the definition of PK Population.

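### SAP 9 summarises PK across dosing schedules, so at any shared dose level the troughs from C2D1, and AUCtau from the C1D15 dose, mix 14-day with 7-day intervals

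*SAP*

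**What the plan says.** The governing sentence is in SAP 9: "Unless otherwise specified, all PK data analysis will be based on the PK population and summarized by dose levels regardless of dosing schedules". Nothing in SAP 9.2 to 9.4 brings schedule back into a summary or figure. Concentrations, PK parameters, box plots and the mean Ctrough plot are all by dose level, and the power model names no schedule term. Schedule appears only as a sort key in the listings (SAP 9.2 and 9.3).

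The two regimens are in SAP 3.1. On Schedule 1, "SL-172154 is given on days 1, 8 and 15 in cycle 1 (28 days for each cycle) and then every 2 weeks thereafter". The other reads "Schedule 2: SL-172154 is given on days 1, 8, 15 and 22 each 28-day cycle". SAP Table 6 ties Ctrough and AUCtau to the dosing interval without fixing its length, and plans accumulation ratios of C1D15 and C2D1 to C1D1.

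Protocol 9.2.3 sets the general rule: "Tabular summaries will be presented by dose levels/schedule/cohorts and total number of subjects in the corresponding population". SAP 11 declares four changes from the protocol. The only one about stratification drops cohort and keeps schedule: "data from different cohorts will be pooled and summarized by schedule/dose level". SAP 5.2 also presents tables by schedule and level, with tables pooled over schedules in addition.

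**The concern.** A trough summary is interpretable only if its values come from the same point in the same kind of interval. After day 15 of cycle 1 that no longer holds across schedules: a predose value on Schedule 1 follows a two-week gap, one on Schedule 2 a one-week gap. A pooled mean at a shared dose level then depends on how many subjects came from each schedule, and it describes neither regimen.

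Protocol 3.3 makes overlap likely once Schedule 2 opens, because its first dose must be one that has completed safety evaluation on Schedule 1. Protocol 3.1.1 has the RP2D decision cover schedule as well as dose, on the totality of the data. Whether weekly dosing raises repeat-dose exposure is a natural question for that decision, and the planned PK summaries cannot answer it. Protocol 6.5.1 adds weight to the troughs, since beyond C3D1 only predose PK samples are taken.

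**Working it through.** **1. Intervals by calendar.** Inputs are the dosing days in SAP 3.1 and protocol 3.3. Schedule 1 doses on study days 1, 8, 15, 29, 43, 57 and so on; Schedule 2 doses every 7 days from day 1. The gap is the sampling day minus the last earlier dosing day.

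| Predose sample | Study day | Schedule 1 gap | Schedule 2 gap |
|---|---|---|---|
| C1D8 | 8 | 7 d | 7 d |
| C1D15 | 15 | 7 d | 7 d |
| C2D1 | 29 | 29 − 15 = 14 d | 29 − 22 = 7 d |
| C3D1 | 57 | 57 − 43 = 14 d | 57 − 50 = 7 d |

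The C2D1 row reproduces protocol 3.3, which ends the 28-day DLT period 14 days after the last cycle 1 dose on Schedule 1 and 7 days after it on Schedule 2. Troughs are therefore like for like through the C1D15 predose sample and unlike from C2D1. The interval that *follows* the C1D15 dose is already 14 against 7 days, so AUCtau is unlike one dose earlier.

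**2. Half-life range.** No human value is given. Protocol 1.2.4 reports monkey values of about 0.4 h (1 mg/kg), 1.1 h (10 mg/kg) and 0.9 h (40 mg/kg). Inclusion criterion 10 expects 30 days to exceed 5 half-lives, which implies less than 30/5 = 6 days.

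**3. Trough ratio at C2D1.** The assumption is linear one-compartment superposition of equal doses. Each dose contributes 2^(−gap/t½).

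- t½ = 6 d, Schedule 1 (gaps 28, 21, 14): 0.039 + 0.088 + 0.198 = 0.326. Schedule 2 adds the 7-day gap: 0.326 + 0.445 = 0.772. Ratio about 2.4.
- t½ = 2 d: 0.0001 + 0.0007 + 0.0078 = 0.0086 against 0.0086 + 0.0884 = 0.097. Ratio about 11.
- At C3D1 the same method gives about 3.2 and 12.

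With equal numbers per schedule, the pooled C2D1 mean is 1.68 times the Schedule 1 value and 0.71 times the Schedule 2 value at 6 days. At 2 days it is 6.2 and 0.54 times.

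**4. AUCtau after C1D15.** The 14-day to 7-day ratio is (1 − 2^(−14/t½)) / (1 − 2^(−7/t½)) = 1 + 2^(−7/t½). This is 1.45 at 6 days, 1.09 at 2 days and 1.01 at 1 day. The C1D1 interval is 7 days on both schedules, so the C1D15/C1D1 ratio carries the same mismatch.

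**5. Can the troughs be measured?** SAP 9.1 gives a lower limit of 10 ng/mL and sets predose values below it to zero. At t½ = 1.1 h, 7 days is 168/1.1, or about 153 half-lives: nothing remains and pooling changes no trough summary. As an illustration, take the monkey Cmax of 1230 ng/mL at 1 mg/kg. At t½ = 1 d, the last dose leaves 1230/2⁷ = 9.6 ng/mL after 7 days, just under the limit. At t½ = 2 d, it leaves the same 9.6 ng/mL after 14 days, so the Schedule 1 trough is borderline.

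**6. Cmax at C2D1.** Adding the residuals to a unit peak gives 1.097/1.0086 = 1.09 at 2 days and 1.772/1.326 = 1.34 at 6 days, well below the trough ratios.

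**The case against.** The strongest reply is that the effect may be nil. Schedule 2 is optional, and the documents do not say whether it enrolled. The only measured half-lives are in monkeys, at about an hour or less, where every trough is zero under the BLQ rule. Serial sampling stops at 48 h on C1D1 and 24 h on C2D1, which fits an expectation of fast elimination. All of this stands, and it makes the size conditional. It does not make the pooling right if Schedule 2 enrols and troughs are measurable.

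Next, SAP 5.2 allows exceptions, protocol 9.2.6 prescribes no stratification for PK, and protocol 9.2.6.1 summarises ADA by dose level. So the departure is from the general rule in protocol 9.2.3 only, and SAP 9 states it openly. What remains is that protocol 9.2 wants deviations documented, and the list in SAP 11 omits this one while saying that summaries keep schedule.

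A reader might infer more than the documents support:

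- *That the schedule effect is lost altogether.* Both the concentration and the parameter listings keep schedule, and SAP 9.4 allows extra predictors in the power model. The loss is in summaries and figures.
- *That these tables would distort the move from Schedule 1 to Schedule 2.* That decision uses Schedule 1 data (protocol 3.2.1 and 3.3), and the SAP 9 data merge follows database lock.
- *That PK and pharmacodynamic tables would not match.* Protocol 9.2.7 has pharmacodynamics "summarized descriptively by dose level, schedule and visit", but the synopsis omits schedule and the pharmacodynamic analysis plan is a separate document.
- *That missed doses cause the same mixing.* This is a separate question. The DLT-evaluable rule does not define the PK population, and cycle 1 dosing is meant to run without deviation.

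**Conclusion.** The point holds for interval-dependent outputs. At dose levels used on both schedules, Ctrough and predose summaries from C2D1, and AUCtau with its accumulation ratios from the C1D15 dose, combine unlike intervals. The planned summaries and figures therefore cannot show whether weekly dosing raised repeat-dose exposure. This affects reporting and the schedule part of the RP2D; it does not touch safety conclusions or the MTD.

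The size is conditional on three things: that Schedule 2 enrols, that troughs are measurable, and that linear superposition is a fair guide. Protocol 3.2 itself raises target-mediated uptake and antibody-driven clearance, so the third is only an illustration. Within the half-life range the documents allow, the C2D1 trough ratio runs from no visible effect at monkey values to about 11 at 2 days (borderline measurable on the illustrative Cmax) and about 2.4 at 6 days. Much larger ratios at shorter half-lives are arithmetically possible, but would probably fall below the assay limit.

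It would be wrong to conclude that all pooling across schedules is unsound. Dosing histories are identical through C1D16, so C1D1 PK, the C1D8 and C1D15 predose samples, and C1D15 Cmax and concentrations can be combined. A mandatory split of later Cmax is not justified: its contrast is much smaller than that of the troughs, and cells are small.

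**What to change.** Amend SAP 9 as follows.

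- Keep pooling across schedules for C1D1 PK, the C1D8 and C1D15 predose samples, and C1D15 Cmax and concentrations through C1D16.
- From C2D1 onward, summarise and plot predose concentrations and Ctrough by schedule within dose level, including the mean Ctrough plot over time.
- From the C1D15 dose onward, summarise AUCtau and its accumulation ratios by schedule within dose level.
- Pooled versions may be shown alongside; a split of Cmax is optional.
- Add the PK pooling that remains to SAP 11 as a change from protocol 9.2.3.

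The cost is a few more outputs and fewer subjects per cell, which matters with cohorts of about three. No new samples are needed. If Schedule 2 did not enrol, one sentence saying so in SAP 9 closes the point.

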9.1 Data Handling

The nominal time relative to the start of infusion will be calculated as the planned time relative to the end of infusion plus the planned infusion duration. The actual time relative to the start of infusion will be calculated as the actual sampling time relative to the start of infusion (SOI) or the SOI of the first infusion period if with infusion interruption(s). Missing PK sampling time will be handled as the following when calculating the actual time relative to SOI:

- If a sampling time is missing and no infusion interruption, the actual time relative to SOI will be calculated as time from SOI to end of infusion (EOI) plus planned time relative EOI.
- If a sampling time is missing and there is interruption(s) during the infusion, the actual time relative to SOI will be calculated as time from the SOI of first infusion period to the EOI of the last infusion period plus planned infusion time relative to EOI.

Concentration values that are below the limit of quantification (BLQ) will be handled as the following:

- If a BLQ value occurs at the predose, the BLQ value will be assigned as zero concentration. If one or more BLQ values occur in a profile after infusion but before the first measurable concentration, the BLQ values will be assigned a value of zero concentration. For linear plots, zero concentration value(s) will be included in the plot. For log-linear plots, zero concentration value(s) will be assigned a missing value.
- If a BLQ value occurs after a measurable concentration in a profile and is followed by a measurable concentration, then the BLQ will be set as missing.
- If a BLQ value occurs after the last measurable concentration in a profile, then the BLQ values will be set as missing.
- If two or more BLQ values occur in succession after a measurable concentration, the profile will be deemed to have terminated at the first BLQ value (BLQ values will be set to missing) and any subsequent concentration will be set as missing.
- BLQ values that are set to be missing will be omitted from PK parameter generation, concentration summary, and the individual PK profile plots.
- For the time point that all concentrations are BLQ and all BLQ results are imputed to be zero, then the mean/median concentration will be reported as zero.
- For the time point that only some concentrations are BLQ and BLQ values are imputed to be zero, the mean/median will be reported unless the mean/median value is below the LLQ (10 ng/ml), in which case the value will be assigned as BLQ.

SL-172154

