9.2 SL-172154 Concentration Measures

SL-172154 concentration values will be sorted by dose level, dosing schedule, sample collection day, and nominal time points in the listing. All SL-172154 concentration values including BLQ will be listed in the same precision as the source data.

SL-172154 concentration will be summarized by dose level for each nominal time point relative to the EOI. Standard summary statistics will be calculated (i.e., mean, standard deviation [SD], median, minimum, maximum, coefficient of variation (CV%), geometric mean, geometric CV%).

Individual subject concentration-time profiles and median/mean profiles by dose level will be plotted for C1D1, C1D15 and C2D1, using the actual time from SOI for individual plots and the nominal time from EOI for medina/mean profiles. Each of the figures will contain one plot on the untransformed scale (i.e. linear plot) and one plot on the log transformed scale (i.e. semi-log plot). For mean concentration profile plot, mean+/- SD for each dose level will be plotted. For median concentration profile plot, median along with minimum and maximum for each dose level will be plotted. Individual subject concentration-time profiles using actual time from SOI (semi-log plot) will also be plotted along with infusion actual start and end time (including any interruptions) for each dose level at C1D1, C1D15 and C2D1.

Dose normalized concentration will be calculated by dividing total administered dose (mg). Mean (SD) dose normalized concentration time profile will be plotted for each dose level at C1D1, C1D15 and C2D1.

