9.4 Assessment of Dose Proportionality

An assessment of dose proportionality will not be based strictly on statistical rule criteria but rather, several factors will be considered when assessing dose proportionality, such as results derived from a Power Model (e.g., the slope estimate, and the width of the 95% confidence intervals), graphical evaluation (box plots of dose-normalized PK parameters) and descriptive statistics of PK parameters by dose, as data permit.

Dose normalized PK parameters will be calculated by dividing total administered dose (mg) for AUC_{0-inf}, AUC_{0-last}, AUC_{tau}, C_{max}, and C_{trough}. Additional dose normalized PK parameters may be calculated, if appropriate and as data permit. Dose proportionality will be evaluated graphically using box plots of dose normalized PK parameters (AUC_{0-inf}, AUC_{0-last}, AUC_{tau}, C_{max}, and C_{trough}) by dose level for C1D1, C1D15 and C2D1.

Dose proportionality will also be evaluated for the AUC_{0-inf}, AUC_{0-last}, AUC_{tau}, C_{max}, and C_{trough} using the power model as data permit. A statistical linear relationship between the ln-transformed PK parameters and the ln-transformed actual dose received in mg will be fitted by using a mixed effect model with ln-transformed dose as a fixed effect and subject as random effect. Additional predictors may be included in the model. The general form of the power mode is described as:

$$Ln(Y) = \beta_0 + \beta Ln (Dose) + \varepsilon$$

where Y represents the pharmacokinetic parameter. Note that $\beta = 1$ would correspond to perfect dose proportionality.

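### Late concentration summaries are biased upward because SAP 9.1 omits trailing BLQ values from them, not only from PK parameter derivation

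*SAP*

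**What the plan says.** SAP 9.1 treats a BLQ result according to where it falls in the profile.

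- Before dosing: "If a BLQ value occurs at the predose, the BLQ value will be assigned as zero concentration". A BLQ result after infusion but before the first measurable value is also set to zero.
- After the last measurable value: "If a BLQ value occurs after the last measurable concentration in a profile, then the BLQ values will be set as missing". A BLQ result between two measurable values is also set to missing.
- Scope of the omission: "BLQ values that are set to be missing will be omitted from PK parameter generation, concentration summary, and the individual PK profile plots".
- Where "only some concentrations are BLQ and BLQ values are imputed to be zero, the mean/median will be reported unless" the result is under 10 ng/mL, that result is shown as BLQ.

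SAP 9.2 then says "SL-172154 concentration will be summarized by dose level for each nominal time point relative to the EOI", using the mean, SD, median, minimum, maximum, CV%, geometric mean and geometric CV%. Mean and median profiles are plotted for C1D1, C1D15 and C2D1, and also: "Mean (SD) dose normalized concentration time profile will be plotted for each dose level at C1D1, C1D15 and C2D1". Individual values, including BLQ, appear in a listing.

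**The concern.** Dropping trailing BLQ values is ordinary practice when an individual's AUC or terminal slope is derived. A summary across subjects at a fixed time is a different matter. There, a trailing BLQ result is not an absent observation: it says that the concentration was below 10 ng/mL. Removing it selects subjects on the outcome being summarised. The fastest-clearing subjects leave the table as they fall below the limit, and the remaining tail looks too high and too flat.

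Characterising the PK is a secondary objective, and PK is among the data reviewed for the recommended Phase 2 dose (Protocol Section 2). The concentration-time table and the mean and median plots are what most readers will look at to judge persistence.

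**Working it through.** **Step 1. Follow each kind of BLQ result through SAP 9.1.**

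| BLQ result | Handling | In the by-time-point summary? | 10 ng/mL print rule applies? |
|---|---|---|---|
| Predose | Zero | Yes | Yes |
| Post-infusion, before first measurable value | Zero | Yes | Yes |
| Between measurable values | Missing | No | No |
| After last measurable value | Missing | No | No |
| Profile never measurable | Not clearly stated; the nearest rule gives zero | Possibly, as zero | If zero, yes |

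The same assay result is thus kept and flagged early in a profile, and removed without a flag late in it. The mean and median plots are not named in the omission bullet, but they display the summary statistics and inherit the effect.

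**Step 2. Direction.** Take six subjects at one late time: 40, 25 and 15 ng/mL and three trailing BLQ results (illustrative values).

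| Treatment of the three BLQ results | Mean | Median | Geometric mean |
|---|---|---|---|
| Omitted, as in SAP 9.1 | 80/3 = 26.7 | 25.0 | 24.7 |
| All just under 10 (highest possible) | 18.3 | 12.5 | 15.7 |
| All zero | 80/6 = 13.3 | 7.5 | not defined |

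Whatever the three true values are, all three statistics are too high under omission.

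**Step 3. Size.** The documents give the limit of 10 ng/mL but no human BLQ fraction and no between-subject CV. I assume log-normal concentrations, CV 50% and 100%, and a BLQ fraction p of 25% and 50%. Let s = √ln(1+CV²), so s = 0.472 and 0.833. Let z_p be the standard normal p-quantile, with Φ and φ the normal distribution and density functions. Ratios of the omission statistic to the all-subject value are:

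- mean: Φ(s − z_p)/(1 − p)
- median: exp(s × z_q), with q = (1 + p)/2
- geometric mean: exp(s × φ(z_p)/(1 − p))

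For CV 50% and p = 0.25, z_p = −0.674, and the mean ratio is Φ(1.147)/0.75 = 0.874/0.75 = 1.17. All results, in ng/mL, true value then value under omission:

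| CV | BLQ | Mean | Median | Geometric mean |
|---|---|---|---|---|
| 50% | 25% | 15.4, 17.9 (1.17×) | 13.8, 16.0 (1.16×) | 13.8, 16.8 (1.22×) |
| 50% | 50% | 11.2, 15.2 (1.36×) | 10.0, 13.8 (1.38×) | 10.0, 14.6 (1.46×) |
| 100% | 25% | 24.8, 30.9 (1.25×) | 17.5, 22.9 (1.30×) | 17.5, 25.0 (1.42×) |
| 100% | 50% | 14.1, 22.6 (1.59×) | 10.0, 17.5 (1.75×) | 10.0, 19.4 (1.94×) |

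These are population values. Averages of six-subject medians would mix in small-sample bias: at CV 100% and 25% BLQ the full-data sample median already averages 19.4 against 17.5.

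**Step 4. The zero-substituted mean.** Its ratio to truth is Φ(s − z_p). At 25% BLQ this is 0.87 and 0.93, or about 13% and 7% low. At 50% BLQ it is 0.68 and 0.80, or 32% and 20% low.

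**The case against.** The case for leaving the rule alone has three parts. Omitting trailing BLQ values is standard for non-compartmental work; that stands and is not criticised here. Every BLQ result appears in the listing, so nothing is hidden; that also stands, but SAP 9.2 names no BLQ count among the summary statistics, and a table reader would have to rebuild it by hand. (Table shells are not in the documents, so a count may yet be shown.) Finally, the size rests on assumed CVs and BLQ fractions; that stands too, although the direction does not depend on them.

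Some stronger readings are tempting and are not supported.

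- *That every late summary covers only subjects at or above 10 ng/mL.* A profile that is never measurable has no last measurable value. It may enter as zero, and the SAP does not settle this.
- *That the monkey data show how soon human samples become BLQ.* A mono-exponential curve from the 1 mg/kg Cmax of 1230 ng/mL with the 0.4 h terminal half-life implies an AUC of 1230 × 0.4/ln 2 = 710 ng·h/mL. Protocol Section 1.2.4 reports a mean AUC0-last of 518. The curve does not fit the documents' own figure, and human kinetics are not given.
- *That the Ctrough dose-proportionality model fails.* SAP 9.4 plans "A statistical linear relationship between the ln-transformed PK parameters and the ln-transformed actual dose received in mg", and a zero trough has no logarithm. But SAP Table 6 defines Ctrough by the end of the dosing interval, so a BLQ trough could be read as zero or as missing. The model is fitted only as data permit, and "An assessment of dose proportionality will not be based strictly on statistical rule criteria". This is an unstated detail with no demonstrated wrong result.

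**Conclusion.** The point holds as a minor flaw in a descriptive analysis. Applied as written, SAP 9.1 biases the by-time-point mean, median and geometric mean upward at post-infusion times where some subjects with a measurable profile have become BLQ. Under the log-normal assumption with CV 50% to 100%, the mean is about 1.2 times truth at 25% BLQ and 1.4 to 1.6 times at 50%. The median is about 1.2 to 1.3 times and 1.4 to 1.75 times. How often such time points will occur in this trial cannot be said from the documents.

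A reader might infer that exposure estimates or dose decisions are distorted. They are not: individual non-compartmental parameters come from each subject's own profile, Cmax is not a trailing value, and escalation and the MTD rest on DLT counts.

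**What to change.** In SAP 9.1, limit the set-to-missing rules, for embedded as well as trailing BLQ values, to non-compartmental parameter derivation and individual profile plots. Embedded values leave the summary through the same bullet, so changing the trailing rule alone would be incomplete. For the by-time-point summaries and the mean and median plots:

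- keep all BLQ values, including those from never-measurable profiles, and show n BLQ/N at each dose and time;
- rank BLQ lowest for the median and print it as BLQ if below 10 ng/mL, with zero for the BLQ member when the middle pair straddles the limit;
- apply the existing zero-substitution and print-as-BLQ rule to the mean;
- report no geometric mean or geometric CV% where BLQ values are present.

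In the six-subject example this gives 3/6 BLQ, a mean of 13.3 and a median printed as BLQ.

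The cost is a few sentences and some table programming. The geometric mean is lost at partly-BLQ points. The bias in the mean changes sign: about 7% to 13% low at 25% BLQ and 20% to 32% low at 50%. No single substitution removes this, but n BLQ/N lets the reader see where it applies.
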